## 5 Statistical methods for Pharmacokinetic (PK) parameters

All participants within the PK analysis set will be included in the PK data analysis.

For participants with protocol deviations affecting the PK analyses, the data will be excluded as described in [Table 4-1](#) above.

The evaluation of the pharmacokinetics (PK) of each individual agent when administered as a single or combination therapy is one of the secondary objectives of this study.

### 5.1 Variables

PK samples will be collected in all participants at the visits defined in the Assessment schedule (see protocol section Table 8-1).

Each study drug will be determined by a validated LC-MS/MS method; the anticipated Lower Limit of Quantification (LLOQ) and method specifics will be listed in the central laboratory manual.

Concentrations will be expressed in mass per volume units and will refer to the free base.

Commercially Confidential Information

PK parameters will be determined using the actual recorded sampling times and noncompartmental method(s) with Phoenix WinNonlin (Version 6.2 or higher). Cmax, Tmax, AUC0-t and other parameters as appropriate will be estimated and reported from the plasma concentration-time data if feasible.

### 5.2 Descriptive analyses

Plasma concentration data will be listed by cohort, treatment, participant, and visit/sampling time point. Descriptive summary statistics will be provided by treatment and visit/sampling time point.

Summary statistics per analyte, per time point will be reported. Summary statistics will include sample size (n), mean (arithmetic and geometric), SD, CV (arithmetic and geometric), median, minimum, maximum

Comercially Confidential Information

The geometric mean and its CV will not be reported if the data includes zero values.

The concentration data may be integrated with data from other studies for population PK analysis in the future and will be reported separately.

Pharmacokinetic parameters will be listed by cohort, treatment and participant. Pharmacokinetic parameters will be summarized by treatment and visit. Summary statistics will include sample size (n), mean (arithmetic and geometric), SD, CV (arithmetic and geometric), median, minimum and maximum. An exception to this is Tmax where sample size (n), median, minimum and maximum will be presented. A geometric mean will not be reported if the data set includes zero values.

### **5.2.1 Graphical presentation**

Arithmetic mean (SD) plasma concentration by time will be plotted on linear-linear scale (all treatments in the same graph).

Overlaying individual plasma concentration by time profile, by treatment will be plotted (one graph per treatment, all participants in the same graph) on linear-linear scale.

Individual plasma concentration by time profile, by participant will be plotted on linear-linear scale (one graph per treatment and participant).

## **5.3 Statistical model, assumptions and hypotheses**

Comercially Confidential Information

An unstructured variance-covariance structure will be used. If the unstructured covariance causes model convergence issues, then other simpler covariance structures will be considered in the following sequence: TOEP, AR(1) and CS. The least squares mean differences between treatments and the associated 2-sided 90% confidence intervals in the logarithmic scale will be obtained at each visit and will then be back-transformed to the original scale to produce the geometric mean ratio (GMR) between treatments and associated 90% CIs at each visit and for each PK parameter. The associated p-value will also be obtained at each visit and for each PK parameter.

## 6 Statistical methods for Efficacy/Pharmacodynamic (PD) parameters

All participants within the efficacy/PD analysis set will be included in the efficacy/PD data analysis.

Data will be excluded from the efficacy/PD analyses in the following cases:

- For participants with protocol deviations affecting the efficacy/PD analyses, the data will be excluded as described in [Table 4-1](#) above.
- For participants that discontinued treatment early, the following *programming rule* will be applied: *Any efficacy assessments that occurred on or after the treatment discontinuation study day, will be excluded from all efficacy/PD data analyses. An exception to this is the Day 85 visit or EOS visit imaging data (MRI and MRE assessments), that will be excluded only if they occurred prior to study day 56 (i.e., imaging assessments that occurred on or after study day 56, will not be excluded from the imaging analyses).*
- Participants with <80% treatment compliance

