Concomitant therapies 	X																		
Adverse events	As required																		
Serious adverse events	As required																		
Comments	As required																		
Study completion information																	X	X	

X Assessment to be recorded in the clinical database

S Assessment to be recorded in the source documentation only

NR Non-remote, i.e. this assessment may not be performed remotely (i.e., must be performed at the originally qualified facilities).

 For treatments with an extended half-life, EOS1 will be required as a standard, non-EOS post-treatment follow up visit, and EOS2 will serve as the EOS visit. For all other treatments, EOS1 will serve as the EOS visit.

 If a participant discontinues study treatment early, the participant should be scheduled for a subsequent visit at which time all assessments at the EOS1 visit should be performed. For treatments with an extended half-life, if a participant discontinues early after EOS1, then the participant should be scheduled for a subsequent visit at which time all assessments at the EOS2 visit should be performed.

 Assessments to be performed pre-dose.

 All participants must fast for at least 8 hours prior to administration of study treatment.

 Visit will be conducted via telephone only. Participants are not required to present to the study site for assessments.

 Informed consent must be provided by all participants before any screening procedures are performed. The DNA assessment is optional and requires a separate informed consent to be signed.

Commercially Confidential Information

 Standard laboratory assays to be used for screening.

8a COVID-19 test highly recommended to be completed within 1 week prior to first dosing, as defined in Exclusion Criterion #29.

 Serum pregnancy tests will be performed at Screening and EOS; urine tests may be used at other time points.

 A complete physical examination is required at Screening, Day 1, Day 85, and at the study completion visit. A focused physical examination can be performed at all other visits where a physical examination is required. Please see protocol [Section 8.4](#) for more details.

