## 4 Statistical methods: Analysis sets

The **safety analysis set** will include all participants that received any study drug.

The **PK analysis set** will include all participants with at least one available valid (i.e., not flagged for exclusion) PK concentration measurement, who received any study drug and with no protocol deviations that impact on PK data.

The **efficacy/PD analysis set** will include all participants with available efficacy/PD data and no protocol deviations with relevant impact on efficacy/PD data.

For all analysis sets, participants will be analyzed according to the study treatment(s) received.

Throughout this document, 'treatment' refers to the treatment arm of a cohort that each participant is assigned to.

For treatments with an extended half-life, EOS1 will be required as a standard, non-EOS post-treatment follow up visit, and EOS2 will serve as the EOS visit. For all other treatments, EOS1 will serve as the EOS visit. If a participant discontinues study treatment early, the participant should be scheduled for a subsequent visit at which time all assessments at the EOS1 visit should be performed. For treatments with an extended half-life, if a participant discontinues

early after EOS1, then the participant should be scheduled for a subsequent visit at which time all assessments at the EOS2 visit should be performed.

The Day 113 (EOS1) visit for treatments with no extended half-lives and the Day 141 (EOS2) visit for treatments with extended half-lives will be pooled and reported/analyzed together under a common EOS visit, labeled as 'EOS', in the reporting/analysis. The Day 113 (EOS1) visit for treatments with extended half-lives will be reported/analyzed as a distinct visit, labeled as 'Day 113', in the reporting/analysis.

For the End of Study (EOS) visit, only data from study completers will be included in the efficacy summary/analysis tables/figures. Safety summary/analysis tables/figures will include data from all participants, i.e., both study completers and non-study completers for the End of Study (EOS) visit.

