**Table 4-1 Protocol deviation codes and analysis sets**

Category Deviation code	Text description of deviation	Data exclusion
Participants are excluded from safety analysis in case of these PDs:		Exclude participant from safety analysis set
INCL01	Written informed consent must be obtained prior to screen procedures	

Category Deviation code	Text description of deviation	Data exclusion
Participants are excluded from PK analysis in case of these PDs:		Exclude participant from PK analysis set
INCL01	Written informed consent must be obtained prior to screen procedures	
OTH13	Additional data collected is not as per effective ICF/Protocol requirement	Exclude only the PK data that the protocol deviation relates to from the visit the protocol deviation occurred on
Participants are excluded from efficacy/PD analysis in case of these PDs:		Exclude participant from efficacy/PD analysis set
INCL01	Written informed consent must be obtained prior to screen procedures	
OTH12	Follow up end of study MRI was not completed within 7 days of treatment discontinuation	Exclude participant from imaging data analyses from the visit the protocol deviation occurred on (for imaging data, visit can be either Day 85 or EOS)
OTH13	Additional data collected is not as per effective ICF/Protocol requirement	Exclude only the efficacy/PD data that the protocol deviation relates to from the visit the protocol deviation occurred on
COMD01	Following randomization initiation of new antidiabetic, insulin, betablockers, thiazide diuretics, fibrates, statins, niacin, ezetimibe, thyroid hormone, psychotropic, estrogen, birth control	Exclude participant from all efficacy/PD analyses from the protocol deviation's study day (i.e., prohibited medication's start day) onwards

Category Deviation code	Text description of deviation	Data exclusion
TRT03	Treatment modification guidelines per protocol not followed	Exclude participant from all efficacy/PD analyses from the protocol deviation's study day onwards – PD is exclusionary only under specific criteria*

\**TRT03 PD is exclusionary if dose interruption is > 2 days and/or decreased dose is continued for > 2 weeks.*

If updates to this table are needed, an amendment to the SAP needs to be implemented prior to DBL.

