### **6.2.3 Statistical model, assumptions and hypotheses**

A mixed-effect model for repeated measures (MMRM) analysis will be conducted for log-transformed ratio to baseline in ELF Test and ALT.

Commercially Confidential Information

An

unstructured variance-covariance matrix will be used to account for correlation among multiple measurements from the same participant and variance heterogeneity. If the unstructured covariance causes model convergence issues, then other simpler covariance structures will be considered. Least squares mean, the associated 2-sided 80% confidence interval and the p-value will be obtained for each treatment at each visit and back transformed to the original scale, meaning that the least squares means will be expressed as geometric means after the back-

transformation on the original scale. Contrasts assessing trend over time will be constructed for each treatment using various functional forms as needed. Both cohort-wise and combined cohort analysis will be performed as appropriate.

Log-transformed ratio to baseline in % liver fat, hsCRP, HOMA-IR, HbA1c, fasting glucose, fasting insulin and fasting lipid profile as well as change from baseline in ELF Test, ALT and % liver fat, waist circumference, hip circumference, waist to hip ratio and percentage change from baseline in body weight will also be analyzed. Parameters with more than one post-treatment measurement will be subjected to the same MMRM analysis described above for ELF Test and ALT using untransformed baseline in lieu of log-transformed baseline as a covariate for the untransformed data analysis.

Commercially Confidential Information

Additionally, a multivariate ANCOVA will be done for the three-dimensional endpoint: log-transformed ratio to baseline in ELF Test, ALT and % liver fat at Week 12. The model will include treatment and stratification factor (race and BMI group at baseline) as classification factors and log-transformed baseline as a covariate. An arbitrary 3 by 3 covariance matrix will be assumed for the three-dimensional endpoint.

If there are sufficient data, then a subgroup analysis (ANCOVA) in participants with baseline liver fat  $\geq 10\%$  will be performed to compare % liver fat between treatments.

Commercially Confidential Information

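### The SAP drops ELF and ALT taken on the day treatment stops, although dosing-visit samples are pre-dose, while MRI up to 7 days later can be kept

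*SAP*

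**What the plan says.** For early treatment discontinuers, SAP section 6 removes the following from every efficacy and PD analysis: "Any efficacy assessments that occurred on or after the treatment discontinuation study day". Day 85 and EOS imaging is treated differently: "imaging assessments that occurred on or after study day 56, will not be excluded from the imaging analyses". Code OTH12 in SAP Table 4-1 limits this by excluding imaging where "Follow up end of study MRI was not completed within 7 days of treatment discontinuation".

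Protocol Table 8-1, footnote 3, attached to Days 1, 15, 29, 43, 57 and 85, reads "Assessments to be performed pre-dose". It is not attached to the EOS visits. Under footnote 2, after an early stop "the participant should be scheduled for a subsequent visit at which time all assessments at the EOS1 visit should be performed".

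Three further provisions matter:

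- SAP section 4 says that for the EOS visit "only data from study completers will be included in the efficacy summary/analysis tables/figures".
- SAP section 6.2.3 says "a multivariate ANCOVA will be done for the three-dimensional endpoint", made up of ELF, ALT and liver fat at Week 12.
- SAP section 6.2.3.1 assumes missing at random for the MMRM. For the multivariate model it allows, but does not require, an analysis carrying forward the last ELF and ALT.

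The readable text does not define the treatment discontinuation study day. SAP section 6 defines a last treatment day, but only for the compliance calculation.

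**The concern.** The rule appears meant to restrict efficacy to on-treatment data, but its boundary is one day too early for blood samples. A participant sampled before dosing at the Day 57 visit and stopped that day has been treated up to the previous dose. Nothing in on-treatment reasoning calls for deleting that sample. The same participant's MRI, taken up to a week off drug, may stay in.

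Two things are at stake. With about 20 evaluable participants per arm, valid last on-treatment values are lost. And if a participant stops because of the value measured that day, deletion removes a high ALT selectively and the arm's mean looks lower than it is. A discontinuer with a retained MRI also has liver fat but no Week 12 ELF or ALT, and the SAP does not say how such partial vectors enter the main multivariate model.

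**Working it through.** The readable documents give no figure for the effect of this rule, so there is nothing to reproduce.

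**1. What happens to each measurement**

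| Measurement in an early discontinuer | On treatment? | SAP result |
|---|---|---|
| ELF/ALT at a dosing visit before the discontinuation day | yes | kept |
| ELF/ALT pre-dose at a dosing visit on the discontinuation day | yes, up to the previous dose | excluded |
| ELF/ALT at the later EOS-type visit | normally no | excluded |
| MRI on or after day 56, within 7 days of stopping | possibly up to 7 days off drug | kept by section 6 and OTH12; in doubt under section 4 if labelled EOS and from a non-completer |

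Only the second row is a wrong exclusion. The third is consistent with an on-treatment analysis.

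**2. When deletion biases ALT**

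Assumed, because no values are readable: true log ALT ratio 0 at Days 15, 29, 43, 57 and 85; SD 0.25 to 0.45; equal correlation 0.5 to 0.7; all stops at the Day 57 visit, in 4%, 8% or 20% of an arm (1/25, 2/25, 5/25). The estimator is large-sample maximum likelihood for monotone normal data, the limit of an unstructured MMRM, on 1,000,000 simulated participants per setting. Bias = 100 × (exp(estimated mean) − 1).

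| Reason for stopping | Day 57 value | Bias, Day 57 | Bias, Day 85 |
|---|---|---|---|
| Random | deleted | about 0% | about 0% |
| High Day 43 value, which is retained | deleted | about 0% | about 0% |
| High Day 57 value, 4% stop | deleted | −1.0 to −2.7% | −0.2 to −0.5% |
| High Day 57 value, 8% stop | deleted | −1.8 to −4.9% | −0.4 to −1.0% |
| High Day 57 value, 20% stop | deleted | −4.5 to −11.0% | −1.0 to −2.3% |
| High Day 57 value, any rate | kept | about 0% | about 0% |

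For scale, the 80% confidence half-width for one arm of 20 is exp(1.2816 × SD/√20) − 1. SD 0.25 gives exp(0.0716) − 1 = 7.4%; SD 0.45 gives exp(0.1290) − 1 = 13.8%.

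**3. A harsher scenario and what it requires**

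Let participants stop at any of the first four visits as soon as ALT crosses a threshold, with SD 0.3 to 0.4 and correlation 0.6 to 0.8. Deleting the stopping value then gives a Day 85 bias of about −2.4 to −4.2% at 10% drop-out and −4.7 to −7.9% at 20%. Those drop-out rates need a threshold of only about 1.5 to 2.1 times baseline. Protocol Table 16-1 requires permanent discontinuation above 3 times baseline (baseline at least 2 × ULN), or above both 3 × ULN and 5 times baseline (baseline below 2 × ULN). At 3 times baseline the same model gives 0.05 to 1.2% drop-out and a Day 85 bias of about 0 to −0.6%. At 5 times baseline the bias is essentially zero.

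**4. Three-part endpoint**

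Protocol section 5 expects about 25 enrolled and 20 evaluable per arm, an implied loss of 1 − 20/25 = 20%, or 5 participants. If all 5 stopped on or after day 56 with a timely MRI, liver fat would exist for up to 25 but Week 12 ELF and ALT for only 20. This is a ceiling: the documents do not say why participants would be non-evaluable, and those who stop earlier lose all three components.

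**The case against.** A reader might infer that the rule biases ALT by several percent and that the missing-at-random assumption fails. The documents do not support that. ALT results come back from a laboratory. Protocol section 16.1 calls for re-evaluation 48 to 72 hours after results are available, and Table 16-1 acts on confirmed elevations. The scheduled value that raises the alarm therefore normally precedes the discontinuation day and is kept, which is the zero-bias case. Two liver discontinuations in an arm (2/25 = 8%) already put enrolment on hold under section 9.2.1. A stop for a symptom biases ALT only if the symptom tracks that day's ALT. These points stand. They leave some room for same-day dependence: investigator-judgement stops and interruptions that are not restarted can occur below the permanent-discontinuation thresholds, and an undefined discontinuation day could be back-dated.

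A reader might also infer that the three-part vector can never be completed. That is too strong, because the SAP offers the carried-forward analysis, though only as an option. Conversely, keeping the same-day sample does not create a Week 12 value for someone who stopped at Day 57.

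Keeping late MRI also has a reason. Liver fat is measured only at baseline and end of treatment, so deleting that scan leaves no post-baseline value, whereas earlier ALT values remain in the MMRM. This explains keeping the scan; it does not explain deleting a pre-dose blood sample.

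**Conclusion.** The point holds as a correctable data-exclusion rule. Section 6 discards on-treatment ELF and ALT whenever the discontinuation day falls on a dosing visit, and the missing definition of that day makes the reach of the rule uncertain.

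A bias towards lower ALT is possible but not shown. It is about zero unless stopping depends on the deleted same-day value, and it should be small at Day 85 given the confirmation step and the Table 16-1 thresholds. Where it did arise it would be larger at the stopping visit, which matters a little because the SAP reports estimates at every visit. All percentages rest on assumed SD, correlation and drop-out, and ELF was not simulated. Efficacy is secondary in a non-confirmatory study, so the weight is modest.

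**What to change.** In SAP section 6:

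1. Define the treatment discontinuation study day by the date of the last dose.
2. Keep ELF, ALT and other non-imaging samples taken up to and including the last-dose day. Also keep the pre-dose sample at the visit where treatment is stopped if the last dose was the day before. Exclude only later values. Replacing on-or-after with after is not enough: if the last dose was the day before the stopping visit, that visit's pre-dose sample would still fall after the defined day and be lost.

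In SAP sections 6.2.3 and 6.2.3.1:

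3. Make the carried-forward analysis definite, using the last on-treatment ELF and ALT for discontinuers whose MRI is retained. State how partial vectors are handled in the main multivariate ANCOVA. ELF and ALT from up to 7 days off drug should not be brought in to match the MRI window, since that would abandon the on-treatment principle.

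Across SAP section 4, Table 4-1 (OTH12) and section 6:

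4. Reconcile the completers-only rule for EOS efficacy with the retention of EOS imaging from early discontinuers. Say whether someone who stops treatment but attends the final visit counts as a study completer.

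This is a free improvement: a few sentences of SAP text, settled before database lock, using samples already scheduled.

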## Glossary of terms

Additional treatment	Medicinal products that may be used during the clinical trial as described in the protocol, but not as an investigational medicinal product (e.g., any background therapy).
Assessment	A procedure used to generate data required by the study.
Biologic samples	A biological specimen including, for example, blood (plasma, serum), saliva, tissue, urine, stool, etc. taken from a study participant.
Clinical Outcome Assessment (COA)	A measure that describes or reflects how a participant feels, functions, or survives.
Coded Data	Personal Data which has been de-identified by the investigative center team by replacing personal identifiers with a code.
Cohort	A set of one or more treatment arms bundled together for review and execution.
Control drug	A study drug (active or placebo) used as a comparator to reduce assessment bias, preserve blinding of investigational drug, assess internal study validity, and/or evaluate comparative effects of the investigational drug.
Core NEXSCOT protocol	Section 1 - Section 16. These are the sections of the NEXSCOT protocol that remain constant over the duration of this platform study.
Discontinuation from study	Point/time when the participant permanently stops receiving the study treatment and further protocol required assessments or follow-up, for any reason. No specific request is made to stop the use of their samples or data.
Discontinuation from study treatment	Point/time when the participant permanently stops receiving the study treatment for any reason (prior to the planned completion of study drug administration, if any). Participant agrees to the other protocol required assessments including follow-up. No specific request is made to stop the use of their samples or data.
Dosage	Dose of the study treatment given to the participant in a time unit (e.g., 100 mg once a day, 75 mg twice a day).
Electronic Data Capture (EDC)	Electronic data capture (EDC) is the electronic acquisition of clinical study data using data collection systems, such as Web-based applications, interactive voice response systems and clinical laboratory interfaces. EDC includes the use of Electronic Case Report Forms (eCRFs) which are used to capture data transcribed from source data/documents used at the point of care.
End of the clinical trial	The end of the clinical trial is defined as the last visit of the last participant or at a later point in time as defined by the protocol.

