 Body height only measured at Screening. Waist and hip circumference (for waist-to-hip ratio calculation) only measured at Baseline and Day 85. Blood pressure and pulse rate will be measured in a sitting position at all marked visits.

 Coagulation panel includes PT/INR and aPTT.

 Fasting glucose and insulin used for Homeostasis Model Assessment of Insulin Resistance (HOMA-IR) calculation. Fasting lipid panel includes total cholesterol, LDL, HDL, and triglycerides. Additional analyses of HDL and LDL sub-fractions, ApoC3, and lipoprotein(a) at these timepoints may be performed depending on the compound under investigation.

 Trough PK samples will be collected at all visits during the treatment period (Day 1 to Day 85). On Day 29 and Day 57, additional samples will be obtained as marked.

 Assessment is only to be performed at EOS if a participant discontinues study treatment and from the study early.

 Assessment may include (

CCI

Commercially Confidential Information

CRP,

CCI

ELF Test).

 ELF Test only.

Commercially Confidential Information

 For orally-administered study medications, participants will be provided with a supply to self-administer for 12 weeks (Day 2 to Day 84).

Study medication will be administered by study staff on marked visit days. Participants should bring all used and unused medications, and diaries, to each visit. For other types of study medications, such as injectable monoclonal antibodies, dose administration will be managed by study staff on marked visit days.

 Orally-administered study medications only.

 Optional assessment.

 If Fibroscan is unavailable, alternative technology to assess liver stiffness may be considered upon consultation with the sponsor.

 Assessment is only to be performed at this visit if a participant discontinues study treatment early on or after Week 8 for any reason and should be scheduled as closely to the last dose of treatment as possible.

 Assessment should be performed after eligibility is confirmed from all other screening/baseline assessments wherever possible. MRE is an optional

assessment. See Imaging Subject Scanning Guide for further instructions.

 VAS assessments for itching of the skin.

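### The SAP keeps or drops early discontinuers' MRI by the day of the scan, not the day treatment stopped, and does not say how that rule fits with OTH12 or the protocol's Week 8 trigger

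*SAP*

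**What the plan says.** Four places bear on whether an early discontinuer's liver-fat scan is analysed.

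- **SAP section 6, general rule.** "Any efficacy assessments that occurred on or after the treatment discontinuation study day, will be excluded from all efficacy/PD data analyses". Day 85 or EOS imaging is excepted: these are data "that will be excluded only if they occurred prior to study day 56". The SAP then restates this positively: "imaging assessments that occurred on or after study day 56, will not be excluded from the imaging analyses".
- **SAP section 6, first bullet, with Table 4-1.** "For participants with protocol deviations affecting the efficacy/PD analyses, the data will be excluded as described in" Table 4-1. Code OTH12 there reads "Follow up end of study MRI was not completed within 7 days of treatment discontinuation", with the consequence "Exclude participant from imaging data analyses from the visit the protocol deviation occurred on". A note adds that the visit may be Day 85 or EOS.
- **SAP section 4.** Efficacy tables and figures for the EOS visit use study completers only. Nothing similar is said for Day 85.
- **Protocol Table 8-1 (footnote 26) and sections 8.3.3 and 8.5.5.** The MRI in the EOS1 column is "only to be performed at this visit if a participant discontinues study treatment early on or after Week 8". Footnote 26 and section 8.3.3 also ask for it to be scheduled as near to the last dose as can be arranged.

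The protocol glossary says of someone who stops study treatment: "Participant agrees to the other protocol required assessments including follow-up". Stopping drug therefore does not by itself end study visits.

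**The concern.** The protocol asks two questions about an early discontinuer's scan: was treatment long enough, and was the scan close to its end? The SAP exception asks neither. It asks whether the calendar had reached study day 56, which mixes exposure with delay. A short exposure followed by a late scan can pass, and a longer exposure followed by an immediate scan can fail.

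OTH12 supplies the missing limit on delay, but it is a protocol-deviation code, so it acts only when someone records a deviation. A participant who stops before Week 8 is not asked for an MRI near the stop, so there may be nothing to record. The SAP also does not say which prevails when OTH12 excludes a scan that section 6 says will not be excluded.

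Percent liver fat has one post-treatment measurement and is analysed by ANCOVA (protocol section 12.5.1). The optional carry-forward analysis covers only ELF and ALT. Keeping or dropping a scan therefore acts directly on the arm mean and on the tabulated proportions with a 30% relative or 5% absolute reduction.

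**Working it through.** **Inputs.** D is the day treatment stopped, taken as the last-dose day (an assumption), from 1 to 84. S is the scan day, from D to 113 (EOS1). The rules are:

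- day-56 rule (SAP section 6): keep if S ≥ 56;
- OTH12 (SAP Table 4-1): keep only if S − D ≤ 7;
- protocol trigger (footnote 26): D ≥ W, where W is the study day meant by Week 8.

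**1. Where day 56 comes from.** 8 × 7 = 56, so the SAP counts elapsed weeks. Table 8-1's column labels run differently: week w starts on day 7(w − 1) + 1, which gives the printed Day 57 for week 9 and Day 85 for week 13. Week 8 would then start on 7 × 7 + 1 = Day 50. However, the multivariate ANCOVA is set at Week 12, which must be Day 85 = 12 × 7 + 1. By that usage Week 8 is 8 × 7 + 1 = Day 57. W is therefore 50, 56 or 57, depending on the reading.

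**2. Day-56 rule alone.**

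- Stop Day 28, scan Day 85: 85 ≥ 56, kept, 85 − 28 = 57 days off drug.
- Stop Day 57, scan Day 85: kept, 28 days off drug.

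**3. Day-56 rule with OTH12 always applied.** S ≥ 56 and S ≤ D + 7 together require D ≥ 49. The longest gap kept is 7 days, and both scans in step 2 are dropped. What remains is an inversion:

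- stop Day 49, scan Day 56 (7 days off): kept;
- stop Day 55, scan Day 55 (0 days off): dropped.

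**4. If OTH12 is not coded, does another rule remove the Day 28 / Day 85 scan?**

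- Compliance below 80% (SAP section 6): compliance = 100 × (expected − missed)/expected, with expected capsules counted only to the last treatment day. A fully adherent Day 28 stopper has missed = 0 and scores 100%. Not removed.
- Completers-only rule (SAP section 4): applies to EOS, not Day 85. Not removed.

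So the scan is kept, as section 6 is written.

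**5. Replacing the rule by D ≥ W and S − D ≤ 7.** Compared with step 3, in (D, S) day combinations:

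| W | Gained | Lost |
|---|---|---|
| Day 50 | 21 (6+5+4+3+2+1; stops on Days 50–55 scanned by Day 55) | 1 (stop 49, scan 56) |
| Day 56 | 0 | 28 (1+2+…+7; stops on Days 49–55 scanned from Day 56) |
| Day 57 | 0 | 36 (28 + 8; adds stop Day 56, scans on Days 56–63) |

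These are combinations of days, not participants.

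**6. Scale, by assumption only.** With 20 evaluable per arm, one scan is 1/20 = 5 points of responder proportion. If a 30% relative reduction were wholly lost off drug, one such scan would move the arm mean by 30/20 = 1.5 points. If all 5 of 25 non-evaluable participants were treatment discontinuers stopping uniformly over 84 days, 5 × 7/84 = 0.42 per arm would stop on Days 49–55. The documents support none of these assumptions.

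**The case against.** The strongest reply is that section 6 lists its exclusions cumulatively. The day-56 exception lifts only the general post-discontinuation exclusion in its own bullet, and OTH12 still applies through the first bullet. OTH12's wording has no Week 8 condition, and its note about Day 85 or EOS shows that it is aimed at these same scans. A reader might infer that the SAP generally admits long-off-drug scans. Read this way it does not: step 3 shows a 7-day ceiling. That part of the reply stands.

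A Day 85 scan after an early stop is also not clearly due. Footnote 2 of Table 8-1 sends early discontinuers to an EOS1-type visit, and MRI there is limited to stops from Week 8. This makes the long-gap case less likely but does not exclude it. The glossary foresees continued assessments, and both SAP rules name Day 85 as a visit at which such imaging may exist.

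Two further inferences are tempting and fail. One is that on-drug scans are discarded: the rule reaches only assessments on or after the discontinuation day, so the dropped scans are same-day or later. The other is that the SAP discards scans the protocol requires. That needs Week 8 to begin on Day 50, which sits badly with Week 12 meaning Day 85. With Week 8 at Day 56 or 57, no protocol-required prompt scan is lost.

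The reply does not settle precedence. It relies on reading the exception narrowly, and on a deviation being coded where the protocol may define none.

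**Conclusion.** The section 6 imaging exception is keyed to the wrong date and does not implement the protocol's trigger. The consequence depends on OTH12:

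- **Coded for every late scan, and given precedence:** kept scans are at most 7 days off drug and the defect is a minor inversion around Days 49–55.
- **Not coded, as may happen for a stop before Week 8, or treated as overridden by section 6:** a Day 85 scan taken weeks after the last dose is analysed as a treatment result, and neither the compliance rule nor the completers-only rule removes it.

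There is also a loose end at EOS. Under Table 8-1, MRI at EOS1 is scheduled only for early discontinuers. Section 6 retains such scans from day 56, while section 4 removes those of non-completers.

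A reader might go further and infer a demonstrated bias in liver fat. The documents give no distribution of stopping or scan days, so neither the number of scans affected nor a bias can be computed, and the figures in step 6 are illustrations. Few participants are likely to be involved, and liver fat is a secondary endpoint in a study described as non-confirmatory. The point merits a clear, inexpensive correction.

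**What to change.** In SAP section 6, replace the day-56 exception with a single rule. For early discontinuers, retain MRI/MRE only if the last dose was on or after the study day that defines Week 8 and the scan was within 7 days of it, the limit OTH12 already uses. Apply this in the program from the dosing and imaging dates, whether or not a deviation was coded.

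Define Week 8 as one study day, used identically in the SAP and in the protocol's MRI instructions (footnote 26, sections 8.3.3 and 8.5.5). The sponsor must choose the day. State how the rule ranks against OTH12 and against the completers-only EOS rule in SAP section 4.

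The cost is a SAP amendment before database lock, a short protocol clarification and minor programming. The trade-off is that some scans from stops just before the cut-off may be lost. If Week 8 is Day 56 or 57, the change recovers no scans and only tightens the rule. If it is Day 50, prompt scans from stops on Days 50–55 come back in.
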